5.2 Handling of Study Interventions

Manual of Procedures for Theta-Burst Stimulation: Appendix 2

Mechanism for Blinding rTMS: Appendix 3

Manual of Procedures for Hypnotic Stroop and Hypnotic Analgesia: Appendix 4

5.3 Concomitant Interventions

5.3.1 Allowed Interventions

Zaleplon, zolpidem, or zopiclone (1 dose) as needed for significant insomnia during the night prior to the scanner sessions or lorazepam (up to 2 mg) for significant anxiety during the day and night prior to the scanner sessions. These medications may be administered up to the night prior to the stimulation session (until 8:00 PM), but not during the morning of the sessions or at any time during the scanning day (100). The use of alternative hypnotics or anxiolytic compounds requires prior approval from the PIs. Hormonal contraceptives are allowed if the subject has been on a stable dose for at least 3 months. Short-term treatments for headaches, allergies, colds, and flu symptoms will be allowed during the study provided the medications utilized have no established psychotropic effects that would be expected to confound interpretation of study outcome measures. These medications may include non-sedating, over-the-counter, or prescription antihistamines, analgesics and decongestants.

5.3.2 Required Interventions

There are no required interventions.

5.3.3 Prohibited Interventions

Any medication administered for the treatment of any psychiatric or neurologic disorder or any other known CNS active drugs, including herbal, over-the-counter, and homeopathic medications, MAOIs, other antidepressants, antipsychotics, stimulants, opiates, pain medications, and mood stabilizers are prohibited during the day prior to and day of the scanner sessions. Use of zaleplon, zolpidem, zopiclone or lorazepam too close to the time of stimulation or beginning a new regimen of hormonal contraception may lead to excluding the subject from the study.

5.4 Adherence Assessment

Because this is a mechanistic trial involving a screening visit and three mandatory scanner visits, adherence will be determined by whether or not the participant arrives to his/her scanner sessions. We will make every effort that every participant completes this protocol and given the limited time commitment, it is likely we will have good study adherence.

6. STUDY PROCEDURES

6.1 Schedule of Evaluations

Assessment	Redcap Screening: Online	Baseline, Enrollment, Randomization: Visit 1 (Day 0)	TMS Target Scan Day	Hypnotic Stroop Scan Day	Hypnotic Analgesia Scan Day
Online Consent	X				
Informed Consent Form 1 (Screening)		X			
Demographics	X				
Screening Forms	X	X	X	X	X
Medical History	X	X			
Current Medications	X	X		X	X
Informed Consent 2 (Full)		X			
Blood Chemistries		X			
Urine Analysis				X	X
Inclusion/Exclusion Criteria	X	X			
Enrollment/Randomization		X			
Stimulation Log				X	X
Concomitant Medications		X		X	X
Adverse Events		X	X	X	X
HIP/SOARS		X		X	X
HIS				X	X
Pain Induction					X
Stroop Task				X	

Table 2: The table includes the schedule for all of the assessments.

6.2 Description of Evaluations

6.2.1 Screening Evaluation

Consenting Procedure

Consenting Processes: There will be three consent processes: one online screening process for absolute contraindications, one consent process for in-person screening, and the other for study procedures. For the first in-person consent process, the clinical research coordinator (CRC) will screen the participant's eligibility for participation in the study. [name] or [name] will consent the participants for the second in-person phase of the consenting process, which involves discussing the risk of the rTMS procedure and MRI scanning. The participant will be consented in the sequence that has been defined by the NCCIH.

Education and Informed Consent Process: The consent process will start with an introductory paragraph that describes the study. This statement will be followed by a description of the purpose of the research. Next, the procedures will be described and the time duration of the procedures and study. The participant will be notified of the discomforts and risks along with the potential benefits. The participant will receive a *Statement of Confidentiality*. The participant will be notified as to the costs for participation (none) as well as the compensation for participation. The participant will be made aware of the research funding source. The participant will be given information regarding the fact that their participation is voluntary. The participant will then be given the contact information for questions or concerns. Finally, the participant will be asked for their signature in order to consent and give permission to be in the research study.

Plan for Review of Consent Document: The signed consent document will be confirmed by [name] or [name] and will be rechecked by the CRC assigned to this study.

Documentation of Signed Consent: The *NCCIH Site Screening and Enrollment Log* will be utilized to record the consent and screening of all subjects and the outcome of each screening. This log will provide a comprehensive list of all subjects who were screened for eligibility and this information will be maintained electronically in REDCAP. Subjects will be recorded as they are consented in order to ensure completeness and accuracy of the data. All subjects who were consented and screened will be included in this log, including screen failures. This log will not contain identifying information. Subjects will be tracked separately on logs in a coded list with a key. Each page will be numbered and maintained in this log in the *Essential Documents Binder*, behind the *Screening/Enrollment Log* tab. Pages will be stored in reverse chronological order, with the newest pages of the log placed at the front of the section. At the conclusion of the study, the final page of the log will be identified by checking the box in the footer.

Screening Visit

During screening, participants will be screened using the following:

Hypnotic Induction Profile (HIP): This is a clinician-administered instrument. Will allow for assessment of level of hypnotizability(113). Those individuals with a score of 0-8 (low-moderately hypnotizable) on the HIP will be selected in order to prevent a potential ceiling effect(26). HIP will be assessed twice during the in-person screening visit.

2010 Fibromyalgia Diagnostic Criteria: This is a clinician-administered instrument. Participants must fulfill diagnostic criteria for FMS(1). This gold-standard assessment will be utilized to ascertain that the participant does in fact meet standardized criteria for FMS. It is important to establish the formal FMS diagnosis to have a homogenous group of participants.

Massachusetts General Hospital (MGH) Antidepressant Treatment Response Questionnaire (ATRQ): This is a clinician-administered instrument. Participants taking SSRIs will be asked if they are willing to discontinue(114). Participants actively taking antidepressants will be offered a wash-out or excluded for theoretical seizure risk(102). This form is an established tool that allows for the assessment of past and current antidepressant use in depression and pain(114).

The Mini-International Neuropsychiatric Interview (M.I.N.I.): The MINI is a short structured diagnostic interview, developed jointly by psychiatrists and clinicians for Diagnostic and Statistical Manual of Mental Disorders-IV (DSM-IV) and International Classification of Diseases (ICD) 10th revision psychiatric disorders. The *M.I.N.I.* was designed to meet the need for a short but accurate structured psychiatric interview for multicenter clinical trials and epidemiology studies and to be used as a first step in outcome tracking in non-research clinical settings(115).

Transcranial Magnetic Stimulation Adult Safety Screen (TASS): This is a participant self-report instrument. Participants will fill out a TASS questionnaire to determine risk of seizure related to rTMS(88). Any identified seizure risk will disqualify the participant. This assessment is utilized in order to minimize the risk of seizure induction with rTMS.

MRI Safety Screening Form: This is a participant self-report instrument. Participant will fill out a MRI Safety Screening Form to determine if the participant is safe to receive an MRI. We will utilize this screening tool to make sure that the participant has no contraindications for MRI that would exclude the participant from participating(89).

Edinburgh Handedness Inventory: This is a clinician-administered instrument. Participants must be right-handed to participate in this study(96). It is standard to restrict rTMS studies to right-handed individuals only due to variability in hemispheric dominance of left-handed individuals.

The Opioid Risk Tool (ORT): This is a brief, self-report screening tool designed for use with adult patients in primary care settings to assess risk for opioid abuse among individuals prescribed opioids for treatment of chronic pain. Patients categorized as high-risk are at increased likelihood of future abusive drug-related behavior (103).

The Brief Pain Inventory: The BPI measures both the intensity of pain (sensory dimension) and interference of pain in the patient's life (reactive dimension). It also queries the patient about pain

relief, pain quality, and patient perception of the cause of pain(116). The BPI has been validated in FMS(117).

Short-Form McGill Pain Questionnaire (SF-MPQ): The SF-MPQ is a shortened version of of the MPQ providing information pertaining to the sensory, affective, and evaluative dimensions of the pain experience.

Ishihara Color Vision Test: The Ishihara color vision test will be administered during the screening visit to ensure normal color vision per inclusion criteria.

Sense of Agency Rating Scale (SOARS): This scale is administered in conjunction with the HIP to assess the subjective experience of the participant during the HIP.

Tellegens Absorption Scale (TAS): This scale is administered during the screening visit to assess the absorption experiences participants have throughout their lives. This scale is shown to be correlated with hypnotizability.

Pain Numeric Rating Scale (PNRS): This scale is administered to assess subjective intensity of pain.

Dissociative Experiences Scale (DES): This scale is administered to assess dissociative experiences participants have throughout their lives.

Screening Complete Form: This checklist includes a list of all of the obtained screening questionnaires to verify participant eligibility and ensure the completion of all required documentation.

6.2.2 Enrollment, Baseline, and Randomization

Enrollment

All participants will be provided a careful consent discussion prior to enrollment.

At the time of the enrollment visit, potential subjects will be provided with a written copy of the current IRB-approved informed consent form.

Due to the nature of a sham-controlled trial, all subjects will need to understand that during the trial, they will be randomized to either the active stimulation condition or the sham stimulation condition.

Case Report Forms: This study utilizes the *NCCIH Case Report Forms* (CRFs) for each subject enrolled into the study to ensure consistent data collection.

Data will be captured by qualified study staff who will perform primary data collection from source-document reviews to case report forms (CRF).

Data will be collected for this study utilizing the following methods:

1. Data will be transcribed from the Electronic Medical Record (EMR-an electronic source that will be available for review) onto the CRF. A copy of the EMR will be printed and placed in the subject's case file as source documentation.

2. Data will be captured directly onto the CRF and transcribed into the EDC system by study staff and paper documentation will be retained and available for review. Data reported in the CRF will be consistent with the source documents and any the discrepancies will be explained.

Baseline MRI Session for TMS Targeting

TMS Target Baseline Scan Session: This scan session includes all of the scans necessary to identify the r-TMS target for subsequent hypnotic pain and hypnotic stroop experimental sessions.

- MRI Acquisition
 - Structural Acquisition (T1): This structural scan is necessary for several reasons: demonstration that the participant's brain is structurally normal, imaging analysis, and rTMS targeting (81).
 - BOLD fMRI Acquisitions
 - Resting State : Task independent BOLD fMRI will be acquired while the participant eyes are open. Individuals with high hypnotizability have been demonstrated to have higher functional connectivity between the dorsolateral prefrontal cortex (DLPFC) and the dorsal anterior cingulate (dACC) (31). Clusters in the L-DLPFC identified to have the greatest correlation with the dACC will be used for r-TMS targeting.

- Thumb Tapping: Alternating right and left thumb tapping will be used to identify the thumb motor area for each participant and may be implemented to make r-TMS intensity adjustments.
- Spectroscopy: Non-invasive magnetic resonance spectroscopy (MRS) will be used to quantitatively measure brain metabolites, including both inhibitory and excitatory neurotransmitters as well as markers of inflammation.

Pre-rTMS Stroop Assessment

Hypnotic Stroop and Non-Hypnotic Stroop Pre-rTMS Scan Session: This session includes all of the pre-rTMS questionnaires, behavioral evaluations and scans necessary to compare to the post-rTMS.

- Medication Washout, Drug Screen, Pregnancy Test Form: This form will be administered at the beginning of each pre-rTMS assessment to ensure medication washout compliancy (if applicable), document drug screen results, and screen for pregnancy (if applicable).
- Hypnotic Induction Profile: This administration of the HIP will serve as the baseline measure for comparison after the rTMS stimulation session(87). HIP will be measured on three separate occasions throughout the stroop assessment visit - 1) immediately following the pre-rTMS stroop MRI session, 2) immediately following rTMS, and, 3) immediately following the post-rTMS stroop MRI session.
- Stroop Task: This administration of the Stroop task will serve as the baseline measure for comparison to the post-rTMS session(32, 118).
- Pre-TMS Hypnotizability Scan Session (1 hour duration)
 - Structural Acquisition (T1): This structural scan is necessary for several reasons: demonstration that the participant's brain is structurally normal, imaging analysis, and rTMS targeting(81).
 - BOLD fMRI Acquisitions
 - Resting State: This is the baseline scan required for the primary endpoint. Individuals with high hypnotizability have been demonstrated to have higher functional connectivity between the dorsolateral prefrontal cortex and the dorsal anterior cingulate cortex (31).
 - Stroop Task: Brain activity while performing conflict tasks has been demonstrated to be different depending on a subject's level of hypnotizability. This baseline would demonstrate the subject's normal functional brain response to the Stroop Task

(32). Functional brain response to the stroop task will be measured following hypnosis (Hypnotic Stroop) and non-hypnosis (Non-Hypnotic Stroop) audio instructions. These acquisitions will be randomized to prevent order effects. Highly hypnotizable individuals can have a loss of the Stroop Effect with specific post-hypnotic instruction (119, 120) which correlates with the reduction in neural activity during conflict (35).

Pre-rTMS Analgesia Assessment

Pre-rTMS Analgesia Session: This hour-long scan session includes all of the pre-rTMS questionnaires, behavioral evaluations, and scans necessary to compare to the post-rTMS.

- Medication Washout, Drug Screen, Pregnancy Test Form: This form will be administered at the beginning of each pre-rTMS assessment to ensure medication washout compliancy (if applicable), document drug screen results, and screen for pregnancy (if applicable).
- Pain Thresholds: Baseline heat-pain thresholds and supra-pain thresholds will be determined for each volunteer based on responses to computer-controlled thermal stimuli delivered to the left forearm with a 30 x 30 mm advanced thermal stimulator (ATS) thermode (Medoc Pathway Model ATS). Thresholds will be measured using a standard method of limits protocol. Specifically, thermal pain threshold and tolerance values will be assessed outside the MRI scanner to identify a moderate pain intensity value that will be applied during the hypnotic and non-hypnotic analgesia MRI scans. The moderate pain intensity value will be used for both pre- and post-rTMS analgesia MRI sessions.
- Hypnotic Induction Profile: This administration of the HIP will serve as the baseline measure for comparison after the rTMS stimulation session(87). HIP will be measured on three separate occasions throughout the stroop assessment visit - 1) immediately following the pre-rTMS analgesia MRI session, 2) immediately following rTMS, and, 3) immediately following the post-rTMS analgesia MRI session.
- Pre-TMS Scans
 - Structural Acquisition (T1): This structural scan is necessary for several reasons: demonstration that the participant's brain is structurally normal, imaging analysis, and rTMS targeting (81).
 - BOLD fMRI Acquisitions
 - Resting State: This is the baseline scan required for the primary endpoint. Individuals with higher hypnotizability have been demonstrated to have

higher functional connectivity between the dorsolateral prefrontal cortex and the dorsal anterior cingulate cortex (31).

- Pain Induction: Functional brain responses to acute, thermally, induced pain, will be measured using the moderate pain intensity value following hypnosis (Hypnotic Analgesia) and non-hypnosis (Non-Hypnotic Analgesia) audio instructions. These acquisitions will be randomized to prevent order effects. Hypnotic analgesia during pain induction has been demonstrated to be instruction specific (38, 44) and produce alterations in functional connectivity (123).

Randomization

The randomization occurs at the time immediately preceding the stimulation session. The stimulation session will be initiated immediately after randomization. We will perform randomization using permuted block to ensure balancing between arms. The operator is instructed to flip the coil to correspond with the key code, but is unclear as to the treatment group.

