Administration: The TMS stimulator (MagPro, Medtronic Functional Diagnostics, Skovlunde, Denmark) will be used to generate repetitive biphasic magnetic pulses. Magnetic pulses will be delivered with a figure-eight-coil (Cool-B65 A/P-Coil). The L-DLPFC will be localized according to previously described procedures where combined functional and structural imaging is utilized to find the area of greatest connectivity with dACC (81). The participant will receive stimulation over the left motor cortex with single pulses in order to determine that individual's motor threshold through measurement of the corresponding muscle twitching of the subject's relaxed abductor pollicis brevis as measured by electromyography (EMG) once and visual inspection once (91). The PEST procedure will be utilized during the MT acquisition portions of the study (90). Once the MT has been determined, the coil will be moved to the neuronavigated L-DLPFC target(81). The handle of the coil will be pointed backwards (45° angle to the sagittal line) and will be fixed to the stimulation arm (30).

Dosing Schedule: A spaced theta-burst technique will be employed that will modulate the neural network node in targeted neural network for the entirety of the scanning session (27-30, 79). Theta burst TMS will be applied over the left dorsolateral prefrontal cortex (L-DLPFC). Two applications of 800 pulses of continuous theta-burst stimulation at 80% of the resting motor threshold will be utilized as this has been demonstrated effective in producing several hours of change in cortical excitability (30) and safe (17). The decision to choose a 15-minute interval is based on the results of the several human experiments using this spaced approach(29, 30) and on long-term depression (LTD) protocols used in animals, where it has been demonstrated that cTBS trains spaced in the order of 10-15 minute intervals generate more persistent LTD (111).

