6.2.5 Post-rTMS (Active and Sham) Evaluations

Post-rTMS Stroop Assessment

Hypnotic Stroop and Non-Hypnotic Stroop Pre-rTMS Scan Session: This session includes all of the post-rTMS behavioral evaluations and scans necessary to compare to the pre-rTMS.

- Hypnotic Induction Profile: This administration of the HIP will serve as the post-rTMS measure for comparison to the pre-rTMS stimulation session.
- Post-TMS Hypnotizability Scan Session (1 hour duration)
 - Structural Acquisition (T1): This structural scan is necessary for several reasons: demonstration that the participant's brain is structurally normal, imaging analysis, and rTMS targeting(81).
 - BOLD fMRI Acquisitions
 - Resting State: This is the scan required for evaluation of the primary endpoint. Individuals with high hypnotizability have been demonstrated to have higher functional connectivity between the dorsolateral prefrontal cortex and the dorsal anterior cingulate cortex (31).
 - Stroop Task: Brain activity while performing conflict tasks has been demonstrated to be different depending on a subject's level of hypnotizability. These scans will demonstrate the subject's functional brain response to the Stroop Task post-rTMS. Functional brain response to the stroop task will be measured following hypnosis (Hypnotic Stroop) and non-hypnosis (Non-Hypnotic Stroop) audio instructions. Randomization of hypnosis and non-hypnosis scan order for each participant will be kept consistent between both pre- and post-rTMS scans. Highly hypnotizable individuals can have a loss of the Stroop Effect with specific post-hypnoitic instruction (119, 120) which correlates with the reduction in neural activity

during conflict (35).

Post-rTMS Analgesia Assessment

Post-rTMS Analgesia Session: This hour-long scan session includes all of the post-rTMS behavioral evaluations and scans necessary to compare to the pre-rTMS.

- Hypnotic Induction Profile: This administration of the HIP will serve as the baseline measure for comparison after the rTMS stimulation session(87).
- Pre-TMS Scans
 - Structural Acquisition (T1): This structural scan is necessary for several reasons: demonstration that the participant's brain is structurally normal, imaging analysis, and rTMS targeting (81).
 - BOLD fMRI Acquisitions

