Valchev	Motor/Somatosensory cortex	BOLD	2.86192037
Valchev	Motor/Somatosensory cortex	BOLD	1.23857467

Table 4: Effect sizes for rTMS induced changes in brain activity as a surrogate for hypnosis (Jiang 2016)(34) modulated by rTMS(159, 161-163).

As our study is a randomized controlled study, in line with the intention to treat principle, our primary analysis will be a straightforward comparison of the active versus sham groups using a linear model. Following the convention in imaging studies, we will conduct our primary analyses treating the contrast (baseline vs post) as one univariate outcome. The univariate model described below can be estimated either using linear regression or analysis of variance procedures.

A continuous outcome Y for individual i ($i=1,2,3,\dots, N$) can be expressed as $Y_i = \alpha + \gamma Z_i + \varepsilon_i$, where α is the mean of the sham group, Z_i is the randomized treatment assignment status (0=sham, 1=active), γ is the treatment effect, and $\varepsilon_i \sim N(0, \sigma^2)$. According to random assignment, the estimate of γ will be interpreted as causal effect of treatment assignment.

We do not expect much variation across our narrowly defined subjects, although some variation is still possible. As a way of sensitivity analysis, we will also analyze the data in the linear mixed effects modeling framework allowing for random intercepts, although this is not customary in imaging studies. The linear mixed effects model described below will be estimated using the maximum likelihood estimation method implemented in SPSS or in Mplus.

The outcome Y for individual i at time point t ($t = 1,2$ for pre and post) is now expressed as

$$Y_{it} = \eta_{0i} + \eta_{1i}W_t + \varepsilon_{it}, \quad (2)$$

$$\eta_{0i} = \eta_0 + \gamma_0 Z_i + \zeta_{0i} \quad (3)$$

$$\eta_{1i} = \eta_1 + \gamma_1 Z_i + \zeta_{1i} \quad (4)$$

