For each run, a first-level general linear model (GLM) will be conducted using FMRIB's improved linear model prewhitening convolved using a boxcar regressor model (101). Across runs and for each contrast, a within-subject fixed effects analysis will be performed. For group analysis, FMRIB's local analysis of mixed effects will be used within a mask of our a priori ROIs dACC and L-DLPFC, thresholded using family-wise error (FWE) corrected $Z > 2.3$; cluster $p < 0.05$. Average contrast of parameter estimate values will be extracted from our ROIs and Spearman's correlations will be calculated between these values and differences in active versus sham rTMS.

Primary Mechanistic Hypothesis: *Active, inhibitory rTMS (cTBS) over L-DLPFC will modulate the neural network that underlies hypnotizability by producing greater increases in functional connectivity between DLPFC and dACC and reduced activity in both L-DLPFC and dACC.*

Connectivity between L-DLPFC and dACC will be assessed with resting state functional connectivity MRI (31, 51) at the baseline time-point and as well as at the post-rTMS time-point for both rTMS conditions (active and sham). It is hypothesized that inhibitory rTMS (cTBS) to DLPFC will result in increased fc between the DLPFC and dACC. Analyses will be restricted to the dACC and L-DLPFC for the Primary Outcome Measure. To determine if the active rTMS condition is specifically associated with change in dACC and DLPFC functional connectivity, a mask restricted to dACC and DLPFC will be utilized to extract the fMRI connectivity data. It is expected that the correlation in active rTMS group over L-DLPFC to be stronger than the correlation obtained in the sham rTMS group. Regression analysis will be used to investigate whether greater connectivity will be present between L-DLPFC and dACC for active versus sham rTMS (cTBS). Activity in both regions will be measured using the fractional amplitude of low-frequency fluctuation (fALFF) of the fMRI signal to measure the amplitude of regional spontaneous activity throughout the brain. (164) It is a ratio of the power spectrum of low-frequency (0.01-0.08 Hz) to that of the entire frequency range, thereby controlling for overall physiological noise.

Relevant Clinical Outcome: *To determine the effect of active, inhibitory rTMS over DLPFC on enhancing hypnotic analgesia.*

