Handling of missing data: We use the same sample twice to achieve enough statistical power with our moderate sample size, not to model the change between scanning sessions. With no longitudinal components, the two groups (rTMS versus sham) will be cross-sectionally compared in our primary aims. The impact of missing data due to attrition is minimal. Further, time between assessments is so narrow that the probability of having cases with missing data (dropout, attrition) is very low. As a way of assessing the impact of missing scan sessions, we will repeat our main analyses treating outcomes measured in the hypnosis scan and in the hypnotic analgesia scan as multivariate outcomes. This will allow us to include all participants in the analysis as long as one of the two scans is available. In this analysis framework, missing data will be handled assuming that it is missing at random conditional on observed scan session data (maximum likelihood estimation). Analyzing the data using both univariate and multivariate analysis approaches will also serve as sensitivity analyses. Additionally, we will include the order of scan sessions in the model to account for the carryover and order effects.

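### Hypnosis/non-hypnosis run order is randomised but absent from the analysis models: a small loss of precision for the task-run secondary outcomes

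*Combined protocol and SAP*

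**What the plan says.** Section 6.2.2 describes a hypnosis and a non-hypnosis acquisition on the Stroop day, and another such pair on the analgesia day. For both days it states: "These acquisitions will be randomized to prevent order effects". Section 6.2.5 fixes the order within each person: "Randomization of hypnosis and non-hypnosis scan order for each participant will be kept consistent between both pre- and post-rTMS scans".

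The analysis is set out in sections 9.2 and 9.7. Section 9.2 says "our primary analysis will be a straightforward comparison of the active versus sham groups using a linear model", and that "we will conduct our primary analyses treating the contrast (baseline vs post) as one univariate outcome". The model written there has an intercept, an arm term and a residual. Section 9.7 extends the same strategy to Secondary Hypotheses A, C and D. For Secondary E, section 9.6.2 compares changes between arms by ANOVA.

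The only order term is in the missing-data paragraph of section 9.7: "we will include the order of scan sessions in the model to account for the carryover and order effects". In that paragraph, sessions means the hypnosis scan and the hypnotic analgesia scan, that is, the two scan days. The January 2024 SAP covers the change in HIP score and the test of the blind, and has no order term.

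**The concern.** The protocol considered order important enough to randomise it within a session, and modelled order between days for carryover. It then left the within-session factor out of every model. Two runs in one session are closer together than two scan days, so the reason given for the day-order term applies at least as well to the runs.

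Two mechanisms could make run order act on the pre-to-post change:

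- **Fading.** Section 9.6.2 (Secondary Hypothesis D) puts the after-effect at about 1 hour, and section 6.2.5 gives the post-rTMS Stroop-day scan session 1 hour. The second run would then fall later in the decay.
- **Carryover.** The word-blindness suggestion is meant to act after hypnosis. If the hypnosis run comes first, the suggestion may reach the non-hypnosis run. If active rTMS strengthens the response, as Secondary Hypothesis D predicts, that carryover would differ before and after stimulation.

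At stake is the precision of the outcomes read from these runs: the Stroop-task outcomes under Secondary C and D, the analgesia-network outcomes under Secondary E, and the in-scanner pain ratings.

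**Working it through.** **The plan's own power figure.** Section 9.2 states power 0.8 for the primary outcome with 40 per arm, d = 0.8 and two-sided alpha 0.05. The normal formula is power = Φ(d/√(2/40) − 1.96). It gives Φ(0.8/0.2236 − 1.96) = 0.947, so the stated figure does not follow from its inputs. That is a separate matter. Power of about 0.8 at 40 per arm corresponds to d of about 0.63, which I use as a reference effect for a task-run outcome.

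**What cancels.** If run order adds the same amount before and after rTMS, the amount drops out of post minus pre. In 4,000 simulated trials per scenario (40 per arm, d = 0.63), power was 0.799 with such an effect and 0.791 with none. The Monte Carlo standard error is √(0.79 × 0.21/4000) = 0.006.

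**What does not cancel.** Suppose order shifts the change by b SD, with half the participants in each order. Leaving order out gives a residual variance of 1 + b²/4. No b is given in the documents, so these values are assumptions.

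Shift in both arms, power = Φ(0.63/(0.2236 × √(1 + b²/4)) − 1.96):

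| b | residual variance | power | loss (points) |
|---|---|---|---|
| 0 | 1.0000 | 0.8044 | 0 |
| 0.2 | 1.0100 | 0.8005 | 0.4 |
| 0.5 | 1.0625 | 0.7803 | 2.4 |
| 0.8 | 1.1600 | 0.7441 | 6.0 |
| 1.0 | 1.2500 | 0.7123 | 9.2 |

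(Rounding to three decimals before subtracting gives 0.3 in the second row.) I take 0.2 to 0.5 as the working range; the last two rows show how the loss grows.

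Shift in the active arm only: the standard error is √((2 + b²/4)/40).

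- b = 0.2: √(2.01/40) = 0.2242, power Φ(0.63/0.2242 − 1.96) = 0.802, loss 0.2 points.
- b = 0.5: √(2.0625/40) = 0.2271, power Φ(0.63/0.2271 − 1.96) = 0.792, loss 1.2 points.
- b = 0.63, as large as the rTMS effect itself: power 0.785, loss 1.9 points.

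**Bias.** The mean estimated rTMS effect was 0.625 to 0.633 in every simulated scenario, against a true 0.63.

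**Chance imbalance.** If order is drawn 50:50 independently of arm (an assumption), the between-arm difference in the share with hypnosis first has SD √(2 × 0.25/40) = 0.112. With b = 0.2 to 0.5, a one-SD imbalance moves the estimate by 0.112 × b = 0.02 to 0.06 SD. The standard error is about 0.22 SD.

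**Power to see an interaction.** With 20 per arm-by-order cell, the standard error of the interaction is √(4/20) = 0.447. For an interaction of 0.63, power is Φ(0.63/0.447 − 1.96) = 0.29.

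**Price of adjusting.** The simulated adjusted model held both order and order-by-arm. Without any order effect its power was 0.783, against 0.791 unadjusted. With b = 0.5 it was 0.778 against 0.765, and with b = 1.0 it was 0.786 against 0.705.

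**The case against.** The best defence is that the design already deals with order. It is randomised and repeated within person, and the outcome is a change score, so a stable order effect disappears. Omitting a covariate from a randomised comparison is valid. Both points stand. They leave only an effect of order on the change.

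The defence can also say that such an effect is not foreseen. A reader might infer from the 1-hour figure that the sponsor expects order to modify the rTMS effect. The documents do not say so: order is randomised only as a precaution, and section 5.1 says the spaced regimen will "modulate the neural network node in targeted neural network for the entirety of the scanning session". Sections 2.2 and 3 likewise choose spaced stimulation so that the effect outlasts the scan. The statements on duration disagree, and fading is a possibility rather than a stated premise. Carryover before rTMS cancels too, unless rTMS changes it, which nothing in the documents shows.

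A reader might also look for a larger loss in a hypnosis-minus-non-hypnosis contrast. Section 9.6.2 does not define Secondary D or E that way. Each compares the run after hypnotic instruction before and after rTMS.

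**Conclusion.** The point holds as a minor one about precision. Run order is randomised and enters no model. For an assumed shift of 0.2 to 0.5 SD in both arms, the loss is about 0.4 to 2.4 power points at d = 0.63 and 40 per arm. It is roughly half that if only the active arm is affected. The true shift is unknown, and if it is zero nothing is lost.

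Two stronger conclusions are not supported. Leaving order out does not bias the average rTMS effect, because order is randomised; the standard error already reflects chance imbalance. The primary result is also not at risk: section 9.6.1 says "Connectivity between L-DLPFC and dACC will be assessed with resting state functional connectivity MRI (31, 51) at the baseline time-point", and that scan is a separate acquisition from the hypnosis and non-hypnosis runs. The pain thresholds that section 6.2.2 takes outside the scanner are not run-based either, and no analysis in the January 2024 SAP would change.

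**What to change.** In section 9.7, next to the order of scan sessions, add one sentence: models of task-run outcomes (the Stroop-task outcomes under Secondary C and D, the pain-run outcomes under Secondary E, and in-scanner pain ratings) include the randomised run order of that day, hypnosis first or second, as a covariate. Report the centred order-by-arm interaction only as an exploratory check, since its power is about 0.29 even when it is as large as the treatment effect. Keep the covariate-only model as the main one, so that the arm coefficient remains the average rTMS effect.

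The cost is one degree of freedom per model and no new data: the order must already be known for each participant in order to be repeated after rTMS. If the task-run outcomes have already been analysed, label the adjusted result as a sensitivity analysis.
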